## RESEARCH PROTOCOL SUMMARY

TITLE:	A single-centre, two-arm, controlled, prospective randomized trial comparing AIRCAST® KNEE CRYO/CUFF™ passive compressive cryotherapy with VPULSE® active compressive cryotherapy after knee arthroplasty surgery
Short title:	ALASKA trial: Assessment of cooling Application poSt Knee Arthroplasty
IRAS number	322564
Device description	
VPULSE®
 
VPULSE® is designed to improve patient outcomes after injury and / or surgery through reduction of pain and swelling, with the aim to reduce the need for medication.
 
The VPULSE® system is used with anatomically designed pads, providing a continuous flow of cold and intermittent dynamic compression therapy.
 
Motorised cold therapy intended to reduce operative site discomfort and inflammation.

Study type	Medical device trial, involving CE-marked devices used for intended purpose.
Study design	Single-centre, two-arm, controlled, prospective randomized trial.
Patient population	
Adult participants who have unilateral knee replacement surgery (knee arthroplasty) and who meet the study inclusion criteria Participants must have the capacity to provide informed written consent and complete patient reported outcome measures.
 
The study has the following sample parameters: standard deviation of 2 cm per cohort, power beta of 80%, alpha p-value of 0.05. Sample size takes into account 30% attrition rate, effect size of 0.75 (mean difference of 1.5cm on 10cm visual analogue scale) based on previous ROBOT trial results.
 
Total of 88 patients:
 
 
- 44 Patients to receive AIRCAST® KNEE CRYO/CUFF™ (current standard care, control arm)
 
- 44 Patient to receive VPULSE® with knee-specific cuff (intervention arm)
 

Primary objective	To determine the level of operation-site related pain experienced at day 2 post-operation and to compare the average pain scores of patients in the AIRCAST® KNEE CRYO/CUFF™ and VPULSE® arm respectively, through administration of 10 cm visual descriptor scale (VDS) for 'at rest' pain.
Secondary objectives	
Post-operative patient-reported outcome measures:
 
Prior to surgery and 24hrs, 3, 5, 12 days, and 6 weeks post-surgery
 
 
- Pain perception, using VDS pain (at rest and walking) and short form McGill pain questionnaire
 
 
Prior to surgery as baseline, and 6 and 12 weeks post-surgery, knee function and quality of life measurements
 
 
- Knee and Osteoarthritis Outcome Score (KOOS)
 
- Range of motion of the affected limb
 
 
Descriptive safety overview at 30 days and 12 weeks post-surgery:
 
 
- Readmitted to theatre and/or hospital
 
- Infection of wound site
 
- Diagnosed with pulmonary embolism or deep vein thrombosis.
 
 
Patient satisfaction survey at 5 days post-surgery

Sponsor	North Cumbria Integrated Care NHS Foundation Trust
Manufacturer & research grant provider	Joint Operations, supplier of VPULSE® active compression & cooling therapy device. Contact: [name], Business Development Manager, [contact] , email [contact] , www.jointoperations.co.uk , [name]
Chief Investigator	[name], consultant Orthopaedic Surgeon. North Cumbria Integrated Care NHS Foundation Trust. Phone numbers: [name], [contact]
Co-investigators	[name], consultant Orthopaedic Surgeon. North Cumbria Integrated Care NHS Foundation Trust, [contact]

	
[name], Orthopaedic Specialist Practitioner, North Cumbria Integrated Care NHS Foundation Trust, [contact]
 
[name] PhD, Science & Innovation Manager, [contact]; [contact] North Cumbria Integrated Care NHS Foundation Trust
 
[name], Orthopaedic Specialist Practitioner, North Cumbria University Hospitals NHS Trust, [contact]
 
[name], Advanced Nurse Practitioner, North Cumbria University Hospitals NHS Trust, [contact]

Organisation where research will take place	
North Cumbria Integrated Care NHS Foundation Trust Orthopaedics Department [name]

Planned timeline	
Recruitment start date (first patient, first visit) 1 Feb 2023 Recruitment end date (last patient, first visit): 31 Dec 2024 Recruitment end date (last patient, last visit): 31 Mar 2025

Protocol version, date	
Version 2.0, dd 23 Jun 2023

## 1. LAY SUMMARY

Osteoarthritis can be treated with knee replacement procedures, where either part or the whole of the knee joint is replaced. For all major knee operations, post-surgery the site of operation can be painful. Increased pain may limit a patient's progress with post-operative mobilisation. Therefore, research is already ongoing in the field of knee surgery to determine if different type of bandaging and cooling of the affected leg post-surgery may improve patient and clinical outcomes. A relatively new method is now available which involves a combination of active compression and cooling, rather than passive compression and cooling. This may reduce pain. This present study aims to assess if active compression and cooling is better than standard passive compression and cooling in terms of keeping a patient comfortable by reducing pain and possibly improving other clinical outcomes too. A total of 88 patients will be recruited and allocated to either standard care AIRCAST® KNEE CRYO/CUFF™ (passive compression & cooling; 44 patients) and new intervention VPULSE® (active compression & cooling; 44 patients); follow-up of patients will be up to 12 weeks post-surgery. Apart from clinical outcomes such as the degree and type of pain experienced by patients, safety data such as incidence of infection and deep vein thrombosis/pulmonary embolism, plus readmission to hospital will be recorded too. The main objective of the study is whether VPULSE® is significantly better than standard AIRCAST® KNEE CRYO/CUFF™ 48 hours post-surgery when measured on a visual display pain scale.

## 2. INTRODUCTION

Major knee surgery is associated with post-surgery pain. The surgical site is subject to bleeding and inflammation-related fluid build-up in the intraarticular tissues (Holm et al, 2020). Pain may impact negatively on recovery time and active early rehabilitation due to physical impairment that it may cause ( Mizner & Snyder-Mackler, 2005). This in turn may increase hospital length of stay and poor patient reported-outcomes (Moretti et al, 2012; Williams et al, 2013). Many service improvement programmes and techniques have been introduced in knee surgery over the years, including means to reduce intra-articular bleeding, tourniquets and medication (Martin et al , 2014). Initiatives in post-surgical management of patients have had mixed outcomes. These include methods such as the use of a cold compress (Morsi 2002), cryotherapy (Adie et al, 2012), elastic bandaging (Hughes et al, 1995) and some types of compression bandaging (Anderson et al, 2008; Charalambides et al, 2005; Jonker et al, 2020).

Sole compression bandage therapy, using mainly two-layer short-stretch bandaging, is established treatment of venous ulcers and lymphoedema (Franks et al, 2004, Pike 2011). External compression is tough to aid venous return and reduces hydrostatic pressure in the leg by (i) improving the efficacy of the calf muscle pump and (ii) moving blood from the superficial to deep venous system, subsequently allowing movement of fluid from the interstitial space. The efficacy in total knee arthroplasty is still unclear due to conflicting results in the literature and heterogeneous methodology (Munk et al, 2013; Pinsornsak P & Chumchuen, 2013; Cheung et al, 2014). In a recent study involving knee osteotomy rather than arthroplasty patients, we showed a marked change in the type and temporal profile of pain experienced by patients post-surgery, see Table 1 (Jonker et al, 2020).

The above evidence regarding compression therapy involves bandaging of the most of the leg (from above knee to below ankle). VPULSE® has developed a device that combines active compression of the knee and cryotherapy. This concept is not necessarily novel; Song and colleagues summarised data from 10 randomised controlled trials, involving 522 patients in a meta-analysis of compressive cryotherapy versus cryotherapy alone in knee arthroplasty patients (Song et al, 2016). The conclusion from said study was that pain levels at up to a week post-operation were lower in the combined cryotherapy group compared to the cryotherapy only group. A 10-cm visual analogue scale for generic pain intensity was commonly deployed; the type of pain was not described in any of the studies. Similarly, cryotherapy reduces pain levels in the majority of studies conducted to date but again this is for generic pain intensity (Thacoor and Sandiford, 2019). A limitation with all treatment modalities (compression, cryotherapy or a combination of the two) is that there is a lot of variation in terms of the devices used and their application (frequency or duration).

In summary, there is a body of evidence that both compression alone, cryotherapy alone, and combined compression cryotherapy can all contribute to lower pain levels in patients after knee arthroplasty. As in the osteotomy study (ROBOT), we will here assess the levels of pain after knee replacement and also the pain profile (what type of pain experienced at what time point) when

patient are either using passive compression cryotherapy AIRCAST® KNEE CRYO/CUFF™ or active compression cryotherapy VPULSE®. The need for contemporary appraisals can be illustrated with one example publication from 2006 in which cryotherapy was compared to epidural for pain control (Kullenberg et al, 2006); the average length of stay in hospital was over 5 days in that study. Nowadays length of stay rarely exceeds 2 days, demonstrating the overall improvements made in managing post-surgery recovery of patients.

### **3. INVESTIGATIONAL DEVICE & INTERVENTION**

#### **3.1 Intervention**

##### **3.1.1 Control (standard care) arm - AIRCAST® KNEE CRYO/CUFF™**

Once the operation is finished, a wound dressing is applied and a standard bandage is applied. It consists of one layer of soft synthetic bandage, stretching from proximal tibia to distal femur covered by a further layer of crepe bandage prior to or after tourniquet deflation, with 50% overlap of each layer. Once transferred to the ward for recovery, this standard bandage will be removed and AIRCAST® KNEE CRYO/CUFF™ cryotherapy is applied to the patient's index knee. This is a sleeve containing iced water and it will be utilised for up to 48 hours post-operation or until patient discharge, whichever of the two is sooner.

The CRYO/CUFF™ is designed to combine the therapeutic benefits of controlled cold compression to minimise hemarthrosis and swelling and reduce pain. The cuff is anatomically designed to completely fit the knee providing maximum coverage of the whole joint and allowing the whole surface area to have the continual cooling benefit of cryotherapy. The cuff is attached to the Gravity Aircast Cryo/Cuff Cooler and will hold water and ice needed for six to eight hours of cryotherapy.

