##### **3.1.2 Intervention arm - VPULSE®**

Once the operation is finished, a wound dressing is applied and a standard bandage is applied. It consists of one layer of soft synthetic bandage, stretching from proximal tibia to distal femur covered by a further layer of crepe bandage prior to or after tourniquet deflation, with 50% overlap of each layer. Once transferred to the ward for recovery, this standard bandage will be removed and VPULSE compression cryotherapy is applied to the patient's index knee. As with standard treatment arm, the VPULSE cuff is applied over the routine surgical wound dressing. The cryotherapy effect is achieved by circulating cold water using a pump rather than gravity-driven cryotherapy with the current Aircast Cryo/Cuff set up that is standard care. The VPULSE also achieves compression by intermittent dynamic compression; this is an approximate pressure of 50mmHG. Further info regarding VPULSE can be obtained from the Joint Operations website:

<https://www.jointoperations.co.uk/buy-online/vpulse/>

Apart from the difference in type of compression & cooling therapy, the protocol for both trial arms is identical. Used knee sleeves will be disposed of in line with local guidelines on disposal of clinical waste.

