### **5.4 Follow-up**

Patients are in the study for a period of 12 weeks. Thereafter, the patient will be followed up as they would be in normal clinical practice. Study visits are aligned to hospital/clinic visits where possible. Baseline data can be collected on the day of surgery (prior the actual operation), and 12 day and 12 week post-surgery data can be collected when the patient attends for standard follow-up in the orthopaedics out-patient department. The data at 24 hrs, day 3, 5, and 12 falls outside these dates. For all outcome measures, data can be collected over the phone, via e-mail or by mail (whichever is preferred by the patient – mail is by use of freepost, to avoid patients incurring any costs). The researcher can also send reminders to the participant regarding the completion of certain outcome data at the aforementioned follow-up time points.

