## 6. SUBJECTS

### 6.1 Anticipated number of research subjects

The sample size calculation does take into account a 30% patient attrition rate (withdrawal and loss to follow-up), since this involves a study with multiple time points for data collection up to 12 weeks. From other similar studies we are aware that loss to follow-up is relatively high in this group of patients. Patients will be recruited from the adult (age 18+) population routinely seen by the evaluating clinical staff members. The primary outcome measure is based on knee/leg (ie wound site) pain experienced 5-days post-surgery based on the VDS pain scale 'at rest'. The hypothetical difference in pain perception is 1.5 on a 10 cm scale which equates to a significant 'minimally clinically important difference' for pain (Kelly 2001; Lee et al 2003; Tashjian et al 2009). The values and differences observed in the ROBOT trial will be used for reference.

The non-parametric two-sided Mann-Whitney u-test is applied because the data is ordinal; 80% power and 5% significance is also applied. A priori power calculations using GPower 3.1 software, result in the following sample size summarized in Table 3.

Analysis will be performed on an intention-to-treat basis, although the number of days that a participant has worn a bandage will be recorded.

Table 4, Sample size calculation

	Mean pain score at 5 days post-op	Standard Deviation
Arm A (hypothetical)	5.0	2
Arm B (hypothetical)	3.5	2
	Power beta of 80%, Alpha p-value of 0.05, Effect size 0.75  Sample size required without any drop-out: 62 Sample size with 30% attrition rate included: 88  Total of 88 patients: 
 
- 44 Patients to receive AIRCAST® KNEE CRYO/CUFF™ device (current standard care, control arm)
 
- 44 Patient to receive VPULSE® (intervention arm)
 
	

The CONSORT guidelines require a statement on the number of patients assessed for eligibility (Schulz, Altman & Moher 2010). The number of patients screened but who did not meet the inclusion criteria or who declined to participate will be recorded, as will any patients who are lost to follow-up (Appendix 3).

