## 8.2 Primary outcome statistics

To determine the level of operation-site related pain experienced at day 2 post-operation and to compare the average pain scores of patients in the control and intervention arm respectively, through administration of 10 cm visual descriptor scale (VDS) for pain.

The study is powered to detect the established minimal clinically important difference (MCID) of 1.5 cm on a 10 cm VDS pain.

The average difference between time points will be calculated per group, 2 days post-surgery being the primary endpoint. 24hrs, 3, 5, 12 days and 6 weeks post-surgery will also be analysed. To compare the groups, the Mann-Whitney U-test will be applied.

To avoid relying on one outcome measure related to pain, at 3, 5, 12 days, and 6 weeks post-surgery pain perception will also be measured using the short form McGill pain questionnaire. Again, to compare groups the Mann-Whitney U-test will be applied.

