### Visual Descriptor Pain score

[figure not shown]
How painful has your leg, the one has been operated on, been **in the last day when resting**:

Please put a vertical line on the numbered bar above. We kindly ask you consider the affected knee when you answer this question.

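### Patients discharged before 48 hours will rate some device-free time in the day-2 pain score, and the planned exposure item cannot show how much

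*Protocol*

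**What the plan says.** Protocol section 3.1.1 gives the end of use for the control device: "it will be utilised for up to 48 hours post-operation or until patient discharge, whichever of the two is sooner". Section 3.1.2 states no end of use for VPULSE and relies on the sentence "Apart from the difference in type of compression & cooling therapy, the protocol for both trial arms is identical".

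On length of stay, section 2 says only that "Nowadays length of stay rarely exceeds 2 days".

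Section 8.2 fixes the endpoint with "2 days post-surgery being the primary endpoint", and the Lay summary asks whether VPULSE is "significantly better than standard AIRCAST® KNEE CRYO/CUFF™ 48 hours post-surgery when measured on a visual display pain scale". The resting scale in Appendix 1 asks about pain "in the last day when resting".

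Section 6.1 specifies intention-to-treat analysis and, on exposure, records only the days on which a bandage was worn. Length of stay in days is collected under section 8.1.

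The primary time point is itself inconsistent. Section 6.1 bases the sample size on "pain experienced 5-days post-surgery based on the VDS pain scale". Table 3 has no day-2 column, and section 5.4 lists no day-2 collection: "The data at 24 hrs, day 3, 5, and 12 falls outside these dates".

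**The concern.** Three provisions do not fit together: device use that can end at discharge, a stay usually of two days or less, and a primary rating that looks back over the day before 48 hours. A patient who goes home before 48 hours rates a mixture of hours with and without the device, and one who goes home by 24 hours rates a window wholly without it.

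The primary objective in section 4.1 is the efficacy of the active device against the passive one. If a material part of the rated window is device-free, a null result has two explanations: the devices do not differ, or they were hardly on during the period rated. The trial would hold no data to tell these apart. Section 3.1 says the standard bandage is removed on the ward before either device is applied, so days of bandage wear do not measure device use. Even if the word is read as meaning the device, whole days are too coarse for an exposure capped at 48 hours.

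**Working it through.** **1. The plan's own figure.** Inputs from section 6.1 and Table 4: means 5.0 and 3.5, SD 2, two-sided Mann-Whitney test, 5% significance, 80% power, 62 patients without drop-out, 88 with 30% attrition.

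- Effect size: d = 1.5/2 = 0.75.
- Noncentral t with n scaled by the asymptotic relative efficiency 3/π = 0.955. At 31 per arm the effective n is 31 × 0.955 = 29.6, the noncentrality is 0.75 × √(29.6/2) = 2.885, and power is 81.0%.
- At 30 per arm power is 79.6%, so 31 per arm (62 in total) is reproduced.
- Attrition: 62/0.7 = 88.6, against 88 stated. The arithmetic is not at fault.

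**2. Device-free share of the window.** For a rating at 48 hours with one-day recall, a patient discharged at T hours (T between 24 and 48) rates (48 − T)/24 of the window off device:

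| Discharge | Share off device |
|---|---|
| 42 h | 6/24 = 25% |
| 36 h | 12/24 = 50% |
| 30 h | 18/24 = 75% |
| 24 h or earlier | 100% |

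**3. Effect on the contrast.** The documents give neither discharge times nor carry-over, so these are scenarios. Assume that the rating is the average over the window, that off-device hours carry no between-arm difference, and that the SD stays at 2. With average off-device share f, the expected difference is 1.5 × (1 − f). Power is computed as in step 1.

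| f | Expected difference | Power, 31 per arm | Power, 44 per arm |
|---|---|---|---|
| 0 | 1.5 cm | 81% | 93% |
| 12.5% | 1.31 cm | 70% | 84% |
| 25% | 1.125 cm | 57% | 72% |
| 50% | 0.75 cm | 29% | 40% |

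For orientation, f = 12.5% arises if a quarter of patients leave at 36 h (0.25 × 0.50), and f = 50% if all leave at 36 h. The 31-per-arm column takes the full 30% loss by day 2; the 44-per-arm column takes none. With full carry-over after removal, the row f = 0 applies whatever the discharge times.

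**4. Dependence on the time point.** In Table 3 the 24-hour rating has a 6-hour tolerance and so reaches 30 h at most. The day-3 rating has a 1-day tolerance and reaches 48 h only at its early edge. If the primary rating were taken at nominal day 3 or day 5, the whole recall day would lie after the 48-hour cap for every patient, and the table above would not apply.

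**The case against.** Much of the case on the other side stands.

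- **Validity.** Comparing each device as used until discharge is a legitimate randomised question, and intention to treat answers it. The difficulty lies in interpretation and possibly in power.
- **Carry-over.** The protocol's rationale points to some. The Introduction cites lower pain up to a week after surgery, section 3.1.1 gives the cuff's purpose as limiting swelling and haemarthrosis, and Table 4 places the planned 1.5 cm at day 5, after the cap. The protocol nowhere defines 1.5 cm as an on-device effect, so no loss at all is possible.
- **Attrition.** The 30% is justified by follow-up to 12 weeks, so loss by day 2 may well be smaller and 31 per arm pessimistic.
- **Partial safeguards.** The 24-hour resting score is already collected and compared between arms, and length of stay is recorded. But nothing says that either will be used to interpret the primary result.

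Two stronger readings are tempting. A reader might infer that most patients will leave within the exposure period; the length-of-stay sentence is background, fits stays of about two days, and gives no distribution. A reader might also infer that VPULSE could run on after discharge while the control stops, so that duration is confounded with device. The sentence calling the arms identical most plainly carries one stop rule to both. The exclusion of patients unable to remove the device themselves covers both arms and does not mention home use. What is left there is an ambiguity of wording.

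**Conclusion.** The concern holds in a limited form. On the protocol's own terms, patients discharged before 48 hours rate some device-free time at day 2, and no planned item would show how much. The randomised comparison of the devices as used is sound; what is weakened is the conclusion that a null day-2 result can support.

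The size cannot be fixed from the documents. It runs from no loss (full carry-over, or everyone on the device to 48 hours) to power of about 29% at 31 per arm, or 40% at 44 per arm, if half the window is off device and off-device hours carry no difference. These are illustrations under stated assumptions and do not predict the trial's power. They also require that the primary time point, given as day 2 in the summary and sections 5.5.1 and 8.2 but as day 5 in section 6.1, with no day-2 rating in Table 3, resolves to 48 hours.

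**What to change.** - Reconcile sections 3.1.1 and 3.1.2 so that the end-of-use wording is explicit for both arms. What the rule should be is for the clinical team.
- Reconcile the primary time point across the summary, sections 5.4, 5.5.1, 6.1 and 8.2, and Table 3, since the recall window depends on it.
- Replace the bandage-days item in section 6.1 with the date and time at which the device was first applied and finally removed.
- Report by arm the share of the primary recall window spent on the device.
- Name the existing 24-hour resting score as the prespecified supportive on-device comparison. Its own recall day may include hours before the device was applied on the ward, so it supports the fixed-time primary and does not replace it.
- Commit to wording a null day-2 conclusion in the light of the exposure reported.

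A rating at final removal, if added, should be descriptive only: its timing follows randomisation and may depend on pain, since patients in less pain may leave sooner.

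The cost is protocol wording, one timed data item in place of a cruder one, and a little extra analysis. No additional visit is needed.
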